###### [2] Anti-ONO-4538 antibody-positive subjects

Subjects with at least one positive sample for anti-ONO-4538 antibodies after the first dose of the investigational product. They will be classified as follows.

1. Persistent positive: Subjects with two or more samples collected at consecutive time points after the first dose of the investigational product and testing positive for anti-ONO-4538 antibodies with a minimum interval of 16 weeks (there is a time window for one week) between the first and last positive samples.
2. Only the last sample positive: Subjects for whom only the last sample is positive for anti-ONO-4538 antibodies.
3. Other positive: Other subjects (not meeting 1 or 2) with samples positive for anti-ONO-4538 antibodies.
4. Neutralizing positive: Subjects with at least one positive sample for anti-ONO-4538 antibodies including neutralizing ones.

### [3] Anti-ONO-4538 antibody-negative subjects

Subjects without any positive sample for anti-ONO-4538 antibodies after the first dose of the investigational product.

### **11.3 Analysis Methods**

The following will be calculated: the proportions of baseline positive subjects, anti-ONO-4538 antibody-positive subjects and anti-ONO-4538 antibody-negative subjects in the Anti-drug Antibody Analysis Set; the proportions of "persistent positive" subjects, "only the last sample positive" subjects and "other positive" subjects among anti-ONO-4538 antibody-positive subjects; and if necessary, the proportion of "baseline neutralizing positive" subjects and "neutralizing positive" subjects among anti-ONO-4538 antibody-positive subjects. The analysis results will be summarized by squamous NSCLC and non-squamous NSCLC separately and totality.

## 12 GENERAL PRESENTATION OF SUMMARIES AND ANALYSES

### 12.1 Summary Statistics

As summary statistics, mean, standard deviation, median, maximum, and minimum will be calculated unless otherwise noted.

### 12.2 Significance Level to Be Used

No significance level is defined because no tests will be performed.

### 12.3 Decimals

When displaying the individual data, the number of significant figures will be as shown below. For the mean, standard deviation, and median, the number of significant figures will be the number of significant figures for the individual data + 1. For example, if the number of significant decimal places for individual items of data is 1, that for the mean, standard deviation, and median will be 2.

- Background factors and efficacy endpoint

Integer value (No decimal places)	One decimal place	Two decimal places
Time from diagnosis date of primary disease to first dose date of the investigational product (days) Age (years)	Height (cm) Weight (kg) BMI (kg/m  )	Percent change in tumor diameter of target lesion (%)

· Laboratory values

Integer value (No decimal places)	One decimal place
White blood cell count (/mm  )	MCH (pg)
Red blood cell count (10  /mm  )	MCHC (%)
MCV (fL)	Hemoglobin (g/dL)
AST (GOT) (U/L)	Hematocrit (%)
ALT (GPT) (U/L)	Platelet count (10  /mm  )
ALP (U/L)	Albumin (g/dL)
γ-GTP (U/L)	Total protein (g/dL)
LDH (U/L)	Total bilirubin (mg/dL)
CK (CPK) (U/L)	Direct bilirubin (mg/dL)
Blood glucose (mg/dL)	Uric acid (mg/dL)
BUN (mg/dL)	K (mEq/L)
Na (mEq/L)	Ca (mEq/L)
Cl (mEq/L)	P (mEq/L)
Neutrophil (/mm  )	CRP (mg/dL)
Lymphocyte (/mm  )	SP-D (ng/mL)
Eosinophil (/mm  )	
Basophil (/mm  )	
Monocyte (/mm  )	
RA (IU/mL)	
KL-6 (U/mL)	
Two decimal places	
Three decimal places	
Creatinine (mg/dL)	Urine specific gravity
Free triiodothyronine (pg/mL)	Thyroid-stimulating hormone (μIU/mL)
Free thyroxine (ng/dL)	

· Vital signs

Integer value (No decimal places)	One decimal place
Systolic blood pressure (mmHg)	Temperature (°C)
Diastolic blood pressure (mmHg)	SpO 2 (%)
Pulse rate (bpm)	

· 12-lead ECG

Integer value (No decimal places)
Heart rate (beats/min)
RR interval (ms)
QT interval (ms)
QTcF (ms)
PR interval (ms)
QRS width (ms)

## 12.4 Subgroup Definitions

Item	Classification
Age (years)	<65, 65 - <75, ≥75
Sex	Male or female
Performance Status (ECOG)	0, 1
Brain metastasis	Yes, No
Bone metastasis	Yes, No
Stage	IIIB, IV, recurrence, unknown or other
NSCLC treatment history (Surgery)	Yes, No
NSCLC treatment history (Radiotherapy)	Yes, No
NSCLC treatment history (Number of treatment regimens)	1, 2
Presence of the anti-ONO-4538 antibody	Positive(Persistent positive/ Only the last sample positive, Other positive), Baseline positive, Negative

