**Table 3-3 Study schedule (for subjects completing the treatment phase)**

Category	At end of treatment phase 	Follow-up phase	
Study day		28 days after final dose or on discontinuation 28 or fewer days after final dose 	Follow-up 
Allowable range (days)	-3 to +3	-7 to +7	-
Visit	V f-0	V f-1	V f-n
Pregnancy test 	○ 	○	
Performance Status	○	○	
Vital signs/weight/percutaneous oxygen saturation	○	○	
Chest X-ray	○	○	
12-lead ECG	○ 	○	
Hematology tests, blood biochemistry tests, urinalysis	○	○	
Immunology/hormone tests	○	○	
Serum drug concentration 	○ 	○	
Anti-ONO-4538 antibody 	○ 	○	
Diagnostic imaging (e.g., CT, MRI)	○	○	○
[REDACTED]	[REDACTED]	[REDACTED]	[REDACTED]
	[REDACTED]	[REDACTED]	[REDACTED]
	[REDACTED]		[REDACTED]
Concomitant drugs/adverse events 	←————→		

1. Women of childbearing potential will undergo urine pregnancy testing.
2. Perform only if the subject proceeds to the follow-up phase within 1 year after the start of investigational product administration (by Cycle 9). Collect sample if possible 6 to 12 weeks after the final investigational product dose.

[REDACTED]

[REDACTED]

[REDACTED]

[REDACTED]

5. Investigate all adverse events and concomitant treatments to the completion of the final tests (other than the survey for 'determination of outcome') specified in the protocol. Beyond the completion of the final tests (other than the survey for 'determination of outcome') specified in the protocol, follow any persisting adverse event for which a causal relationship with the investigational product cannot be ruled out, adverse events that resulted in discontinuation, and the concomitant treatments associated with those events until the events resolve, improve, or are determined to be permanent or

no further follow-up is necessary. And all treatment-related adverse events will be followed every 2 weeks if possible.

6. Information from a prior measurement may be included if the day of that measurement falls within the acceptable range at the end of the treatment phase or discontinuation. Unless medically necessary, vital signs will be measured no sooner than 2 days, diagnostic imaging (e.g., CT, MRI) performed no sooner than 15 days, and other tests no sooner than 8 days after the previous measurement.

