## 5 DOCUMENTATION OF STATISTICAL METHOD

### 5.1 Efficacy Endpoints

#### 5.1.1 Primary Endpoint

1. Response rate (centrally assessed)

The response rate is the percentage of subjects given a best overall response assessment of CR or PR by the central imaging analysis facility.

In the overall response order of CR > PR > SD > PD > NE, the following criteria will be used to assess the best overall response from the overall response assessments made to the completion of the study. When the definitions of more than one response category are satisfied, the better of the two will be selected as the best overall response according to the order of CR > PR > SD > PD > NE.

- CR: Assessment of CR at least 2 consecutive times in intervals of 4 weeks (28 days) or longer.
- PR: Assessment of PR or greater (CR or PR) at least 2 consecutive times in intervals of 4 weeks (28 days) or longer.
- SD: The best overall response is neither CR nor PR but no overall response of PD is assessed 6 or more weeks after the start of treatment and at least one overall response of SD or better is assessed.
- PD: The best overall response is not CR, PR, or SD, and the overall response is PD.
- NE: The best overall response, which is not CR, PR, SD, or PD, is not evaluable.
- Without target lesions: there is target lesion in investigator assessment but not in central assessment.

The following overall responses will not be used to assess the best overall response:

- Overall response following the start or the end of follow-up of a subsequent NSCLC therapy
- Overall responses after an assessment of PD is made

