#### 2) Data Handling

Background factors shown in Section [12.4 Subgroup Definitions](#) will be used as risk factors. Classification according to risk factors will be based on clinical significance or dividing the sample size into two or three nearly equal parts etc.

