#### **10.1.4 Subgroup Analysis of Safety Endpoints**

Incidences of select adverse events and adverse drug reactions will be analyzed in subgroups. Risk factors and classification methods using these factors will be based on items established in Section [9.2.5 Subgroup Analysis of Efficacy Endpoint](#). The analysis results will be summarized by squamous NSCLC and non-squamous NSCLC separately and totality.

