###### [2] Anti-ONO-4538 antibody-positive samples

Samples were obtained within 100 days of final dose meeting either of the following criteria:

1. Samples after the first dose of the investigational product (collected from subjects who tested negative for anti-ONO-4538 antibodies at baseline) testing positive for anti-ONO-4538 antibodies.
2. Samples after the first dose of the investigational product (collected from subjects who tested positive for anti-ONO-4538 antibodies at baseline) testing positive for anti-ONO-4538 antibodies and with titers at least 4-fold higher than those at baseline.

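### SAP 12.4 treats post-dose antibody status as a background factor: a separate *persistent positive* row would favour subjects sampled longer, and the *baseline positive* and *negative* classes overlap

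*SAP*

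**What the plan says.** SAP 12.4 includes the item "Presence of the anti-ONO-4538 antibody" with the classification "Positive(Persistent positive/ Only the last sample positive, Other positive), Baseline positive, Negative". SAP 9.2.5 calls the 12.4 items background factors, which "will be used as risk factors" for the centrally assessed response rate. SAP 10.1.4 takes the same factors over to safety: "Incidences of select adverse events and adverse drug reactions will be analyzed in subgroups".

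SAP 11.2 defines the classes:

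- *Persistent positive*: two or more positive samples at consecutive time points after the first dose, "with a minimum interval of 16 weeks (there is a time window for one week) between the first and last positive samples".
- *Baseline positive* (main definition): positive at baseline, with no positive sample after the first dose.
- *Negative*: no positive sample after the first dose. Baseline status is not mentioned.

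For samples after treatment, Table 3-3 schedules one 28 days after the last dose and adds in note 2: "Collect sample if possible 6 to 12 weeks after the final investigational product dose". SAP 11.2 (1) limits what counts as a positive sample: "Samples were obtained within 100 days of final dose meeting either of the following criteria". Dosing continues until investigator-assessed progression (SAP 3.4). Response must be confirmed; for PR, 5.1.1 requires "Assessment of PR or greater (CR or PR) at least 2 consecutive times in intervals of 4 weeks (28 days) or longer".

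**The concern.** A subgroup factor for response should be fixed before response can influence it. Here subjects who respond stay on treatment longer, are sampled longer, and so have more opportunity to show positives 16 weeks apart. A higher response rate among *persistent positive* subjects could then be read as evidence that antibodies are harmless or even helpful, when it only reflects sampling time. The SAP gives no landmark, time-dependent method or caveat for these tables.

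The class definitions raise a second problem. If one subject fits two levels of the same factor, two programmers can follow the SAP and produce different tables.

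**Working it through.** The SAP gives no figure for the antibody subgroups. The only plan figures used here are the expected response rates in 3.7.2, which reproduce: squamous (4+5)/(18+21) = 9/39 = 23.1%; non-squamous (5+7)/(19+37) = 12/56 = 21.4%. Weighted by planned size: (41 × 0.231 + 52 × 0.214)/93 = 20.6/93 = 22.1%.

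**Step 1: span required.** 16 × 7 − 7 = 105 days. The first post-dose antibody sample is on Day 15 (Table 3-1), so a positive sample on Day 120 or later is needed. Nominal on-treatment samples (Tables 3-1 and 3-2) fall on Days 15, 29, 43, 99, 127, 169, 253 and 337. The first that qualifies is Day 127.

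**Step 2: span available, by day of progression.** Nominal days; last dose = progression scan − 14; spans counted from Day 15.

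| PD scan | Last dose | 28-day sample (span) | 6–12-week sample (span) | 100-day limit (span) |
|---|---|---|---|---|
| Day 43 | 29 | Day 57 (42) | Days 71–113 (56–98) | Day 129 (114) |
| Day 85 | 71 | Day 99 (84) | Days 113–155 (98–140) | Day 171 (156) |
| Day 127 | 113 | Day 141 (126) | Days 155–197 (140–182) | Day 213 (198) |

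With progression at Day 43, a subject qualifies only through a sample later than the 6–12-week target but within 100 days of the last dose. With progression at Day 85, the optional sample within the target can suffice. A confirmed response needs two scheduled scans, at the earliest Days 43 and 85. A responder dosed until progression therefore progresses on Day 127 or later, and the routine sample alone gives at least 126 days. This assumes that central and investigator readings agree.

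**Step 3: illustration of size.** Let r = 22.1%, s = share of responders sampled long enough, and q = the same share among non-responders. Neither s nor q is in the documents. If antibody formation is unrelated to response, the response rate among those able to qualify is rs / [rs + (1 − r)q].

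| | q = 0.3 | q = 0.5 | q = 0.7 |
|---|---|---|---|
| s = 1 | 48.7% | 36.3% | 28.9% |
| s = 0.9 | 46.0% | 33.9% | 26.8% |

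Example (s = 1, q = 0.5): 0.2215/(0.2215 + 0.7785 × 0.5) = 36.3%.

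**Step 4: pooled reading.** *Last sample only* can favour subjects whose sampling stopped soon after antibodies appeared. Longer sampling would have added a negative sample and moved them to *other positive*. Pooling can therefore shrink or reverse the excess. A simulation with no antibody effect and 22% overall response used 168 combinations of assumed antibody kinetics, optional-sample uptake, progression times and dosing beyond progression. It gave 30–64% for the separate class. The pooled class gave 7–48%: above 22% in 144 combinations, and 7–11% in the 24 with late, short-lived antibody.

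**Step 5: select adverse events.** Longer exposure adds events, but events that stop treatment shorten sampling. SAP 3.6 stops treatment for Grade 2 or higher interstitial lung disease, which is a select term in Addendum 1. In one assumed reference case, incidence in *persistent positive* versus overall was:

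- 57% v 43% with 0.1 events per month and none stopping treatment;
- 42% v 43% with the same rate and all stopping treatment;
- 8% v 15% with events confined to month 1 and half stopping treatment.

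**Step 6: overlap.** Applying the main definitions in 11.2 (2):

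| Baseline | Post-dose positive sample | Classes met |
|---|---|---|
| − | no | Negative |
| − | yes | Positive |
| + | no | Baseline positive **and** Negative |
| + | yes | Positive |

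The third row includes a baseline-positive subject whose later titres rise less than 4-fold, because 11.2 (1) does not count those samples as positive. With b such subjects among N, the three proportions in 11.3 sum to 100% + b/N. For an assumed b = 5 and N = 96 (the treated number in 14.4), that is 101/96 = 105%.

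**Step 7: analysis set.** Efficacy subgroups fall under 9.2, which uses FAS, i.e. all treated subjects. Antibody classes are analysed in ADAS, which needs a baseline and at least one post-dose result. 12.4 has no level for treated subjects outside ADAS.

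**The case against.** The separate row may never be printed. Elsewhere in 12.4 commas mostly separate levels, so the slash can be read as pooling *persistent positive* with *last sample only*. On that reading no direction can be claimed. SAP 11.3 lists the classes separately, so the question is open. This objection stands, and the claim about direction is limited to a separate row.

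The overlap may be harmless. *Positive* and *negative* alone partition ADAS, *baseline positive* could be an extra descriptor, and nothing says that the proportions sum to 100%. *Neutralizing positive* already overlaps other classes. That is a fair reading of 11.3, but 12.4 presents the three as levels of one factor, which a reader will take as exclusive.

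A reader might infer that early progressors can never be *persistent positive*. The documents do not support this. The 100-day limit admits a Day 129 sample, a span of 114 days, and visit windows and treatment beyond progression (3.6) also let some in. Non-responders with long stable disease qualify as easily as responders. The effect is enrichment, not exclusion.

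A reader might also infer that the section 11 analysis counts subjects without any post-dose sample as *negative*. ADAS already excludes them; the gap concerns 12.4 only.

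Finally, 9.2.1 calls the secondary analyses exploratory, 12.2 rules out tests, and the classes will be small: 3 responders among 8, for example, has a Wilson interval of 14–69%. This stands and limits the severity.

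**Conclusion.** The point holds and is minor. Post-dose antibody status is not a background factor. As its own row, *persistent positive* is expected to show a response rate above the overall rate without any antibody effect, because the routine samples give early progressors 42 or 84 days against the 105 required, and confirmed responders dosed until progression at least 126.

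That direction rests on nominal timing, dosing until progression, agreement between central and investigator readings, and antibody formation unrelated to response. The size depends on kinetics and retention that the documents do not give, so the percentages above are illustrations. The simulation also allows no responder to progress before Day 127, which partly builds in its consistent direction.

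The class overlap and the missing row in 12.4 follow from the wording alone; only the 105% needs an assumed count. Nothing here supports a claim that the primary response analysis is biased, or that select adverse event rates are pushed in one particular direction.

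**What to change.** 1. In 12.4, replace the antibody row with status in the baseline sample only: positive, negative, not determined.
2. Report post-dose status against response or select adverse events outside the 12.4 subgroups, in ADAS. Use either a prespecified landmark that counts only later outcomes, or a summary labelled as post-baseline and not causal. State whether *persistent positive* and *last sample only* are separate rows.
3. In 11.2, make the classes mutually exclusive by adding to *negative* the condition that the subject was not positive at baseline. Rename class [1] *baseline positive without post-dose positive* in 11.2 and 11.3.

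The cost is SAP wording and reprogramming of one subgroup row and the 11.3 table; no data collection changes. The baseline-positive row may be small and say little. A landmark uses fewer subjects. The labelled summary keeps more subjects but leaves the bias in the numbers.

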## 12.5 Site Pooling Method

NA

## 12.6 Software for Statistical Analysis

To display analysis, tabulation, and part of figures and tables, SAS Ver. 9.3 or higher, SAS institute, Cary, NC, USA will be used.

For lists, figures, and tables, Microsoft Word will be used.

## 13 INTERIM ANALYSIS

No interim analysis will be performed

## 14 DATA REVIEW

### 14.1 Objectives

After data collection, a preliminary inspection will be performed using unlocked data to examine whether to accept data and subjects, possible variable transformation, definitions of outliers, classification by stratification factors, and others and thereby to decide an appropriate analysis method compatible with data.

### 14.2 Analysis Set

Analysis will be performed in subjects receiving the study drug.

### 14.3 Analysis Items and Data Handling

#### 1) Analysis Items

##### (1) Background factors

Demography

##### (2) Efficacy endpoints

Response rate and progression-free survival (investigator-assessed)

##### (3) Safety endpoints

Summary of TEAE and Incidence of TEAEs by SOC and PT

#### 2) Data Handling

All items will be handled as defined previously in the analysis policy.

### 14.4 Analysis Methods

- 1) The analysis results will be summarized by squamous NSCLC and non-squamous NSCLC separately and totality.
- 2) Summary statistics and frequency distribution of background factors will be calculated, and classification will be decided.
- 3) The response rate (investigator-assessed) and its 95% confidence interval (Wilson) will be calculated to examine the appropriateness of the analysis method. In addition, missingness will be evaluated as necessary.
- 4) For progression-free survival (investigator-assessed), a Kaplan-Meier curve will be presented. In addition, using the Kaplan-Meier method, the median and its 95% confidence interval and

progression free survival rates at 3 and 6 months and its 95% confidence interval will be estimated for the validation of the analysis methods or handling of data.

- 5) Incidences of adverse events will be calculated. In addition, incidences of adverse events by SOC or by PT will be summarized according to Grade.

The above analyses were performed using the data obtained from 96 subjects treated with the study drug as of Feb. 27, 2015.

## 15 CHANGE FROM PROTOCOL

### 1) 4.1 Definitions of Groups 1) Enrolled Set (ENR)

#### (1) Content of change

The Enrolled Set (ENR) was added.

#### (2) Reason for change

The Enrolled Set (ENR) will be evaluated for subject without administration as an analysis population.

### 2) 8.2 Analysis Items and Data Handling 1) Background Factors

#### (1) Content of change

Tumor diameter of target lesion was deleted.

#### (2) Reason for change

As part of the efficacy analysis, analysis of the development of tumor diameter and evaluation of baseline characteristics will be performed.

## 16 SAS PROCEDURE FOR ANALYSIS

### 16.1 95% confidence interval (Wilson)

```
PROC FREQ DATA=[Analysis data set];  
  TABLES [Binary data] / BINOMIAL(WILSON) alpha=0.05;  
  BY [Histologic type];  
RUN;
```

### 16.2 Kaplan-Meier curve

```
PROC LIFETEST DATA= [Analysis data set] METHOD=KM CONFTYPE=LOGLOG;  
  TIME [Time to onset of initial event or censoring] * [Censoring variable]([Censoring value]);  
  STRATA [Histologic type];  
RUN;
```

**Addendum 1 List of Select Adverse Events**

Category	Subcategory	Preferred Term
Endocrine Adverse Events	Adrenal disorder	Adrenal insufficiency Adrenal suppression Blood corticotrophin decreased Blood corticotrophin increased Hypothalamic pituitary adrenal axis suppression Secondary adrenocortical insufficiency
	Diabetes	Diabetes mellitus Diabetic ketoacidosis Latent autoimmune diabetes in adults
	Pituitary disorder	Hypophysitis
	Thyroid disorder	Autoimmune thyroiditis Blood thyroid stimulating hormone decreased Blood thyroid stimulating hormone increased Hyperthyroidism Hypothyroidism Thyroid function test abnormal Thyroiditis Thyroiditis acute Thyroxine decreased Thyroxine free decreased Thyroxine free increased Thyroxine increased Tri-iodothyronine uptake increased
Hypersensitivity/Infusion Reactions		Anaphylactic reaction Anaphylactic shock Bronchospasm Hypersensitivity Infusion related reaction
Gastrointestinal Adverse Events		Colitis Colitis ulcerative Diarrhoea Enteritis Enterocolitis Frequent bowel movements Gastrointestinal perforation

Hepatic Adverse Events	Acute hepatic failure Alanine aminotransferase increased Aspartate aminotransferase increased Autoimmune hepatitis Bilirubin conjugated increased Blood bilirubin increased Drug-induced liver injury Gamma-glutamyltransferase increased Hepatic enzyme increased Hepatic failure Hepatitis Hepatitis acute Hepatotoxicity Hyperbilirubinaemia Liver disorder Liver function test abnormal Liver injury Transaminases increased
Pulmonary Adverse Events	Acute respiratory distress syndrome Acute respiratory failure Interstitial lung disease Lung infiltration Pneumonitis
Renal Adverse Events	Blood creatinine increased Blood urea increased Creatinine renal clearance decreased Hypercreatininaemia Nephritis Nephritis allergic Nephritis autoimmune Renal failure Renal failure acute Renal tubular necrosis Tubulointerstitial nephritis Urine output decreased

Skin Adverse Events	Blister Dermatitis Dermatitis exfoliative Drug eruption Eczema Erythema Erythema multiforme Exfoliative rash Palmar-plantar erythrodysaesthesia syndrome Photosensitivity reaction Pruritus Pruritus allergic Pruritus generalised Psoriasis Rash Rash erythematous Rash generalised Rash macular Rash maculo-papular Rash papular Rash pruritic Skin exfoliation Skin hypopigmentation Skin irritation Stevens-Johnson syndrome Toxic epidermal necrolysis Urticaria Vitiligo
---------------------	---

MedDRA version 17.1
